**Risk Stratification and Early Alerting Regarding COVID-19 Hospitalization (Risk SEARCH)**

**Risk Stratification and Early Alerting Regarding COVID-19 Hospitalization (Risk SEARCH)**

**Study team:** Co-Principal Investigators: **[name], [name] & [name]**

Trial Manager: [name]

Co-Investigators: [name], [name], [name], [name], [name], [name]

**Affiliations:**  Current Health

 Biomedical Advanced Research and Development Authority, U.S. Department of Health and Human Services

**Sponsor:** Current Health, [name]

**Funder:** Biomedical Advanced Research and Development Authority  
U.S. Department of Health and Human Services

**Short title:** Risk SEARCH

**Overview:** In the proposed research, we will use Current Health's remote monitoring wearable device to create novel algorithms to help us predict the progression and severity of COVID-19 in individuals that have recently become infected in the community. Risk scores based on demographics, or for patients in hospital, already exist. However, by using continuous remote patient monitoring, in combination with machine learning and data analysis, we hope to both predict and detected changes in the risk of an individual infected with COVID-19 requiring hospitalization, intensive care unit (ICU) treatment, or death based on their vital signs while still in the community.

## **Risk Stratification and Early Alerting Regarding COVID-19 Hospitalization (Risk SEARCH)**

### **Overview**

In the proposed research, we will use Current Health's remote monitoring wearable device to create novel algorithms to help us predict the progression and severity of COVID-19 in individuals that have recently become infected in the community. Risk scores based on demographics, or for patients in hospital, already exist. However, by using continuous remote patient monitoring, in combination with machine learning and data analysis, we hope to predict the risk of an individual infected with COVID-19 requiring hospitalization, intensive care unit (ICU) treatment, or death based on their vital signs while still in the community.

We plan to use a pilot and two-stage approach, including an observational stage to ‘train’ a predictive algorithm and a validation stage to test its efficacy. In the pilot stage, we will recruit up to 50 participants to test the recruitment pathway, trial logistics, and to begin model building. In stage one, the training stage, we plan to recruit 1000 study participants, who will contribute information from the remote monitoring device, demographic data, and daily questionnaires on symptoms they experience. This information will help our data scientists train a dataset using machine learning and algorithm development techniques. In the second stage, we will validate or test that algorithm on a different sample of up to 1000 study participants. Based on current epidemiological data, the recruitment of this number of participants in each stage should provide us with 100 events/hospitalizations in each cohort (see Graph 2, below).

[figure not shown]
Using a hospital-grade home-based, remote monitoring wearable gives us the opportunity to create a unique and extremely useful tool in predicting and managing the clinical effects of the COVID-19 pandemic. Our algorithm might bridge the gap between demographic models and in-hospital models of disease progression by providing real-time data from the community. If we are successful, this tool could be made available immediately to enable better resource allocation for patients after diagnosis. In addition, it enables patient-centered management, increasing confidence for low and high risk patients, and those managing their care. The results of this research will provide a database that can be used in future trials to assess treatment efficacy and offer the potential for rapid algorithm iteration in the event of a future pandemic.

## Background

### *Landscape of SARS-CoV-2/COVID-19*

[figure not shown]
SARS-CoV-2/COVID-19 is a highly contagious virus that has rapidly spread across the globe, with the United States among the countries consistently reporting the highest number of cases. Emerging reports of risk factors for hospitalization and death in patients infected with SARS-CoV-2/COVID-19 include increasing age, BMI > 40, being male, and having diabetes, among others. CDC data from the first month of the SARS-CoV-2/COVID-19 outbreak in the United States showed that the absolute number of hospitalizations per age group is similar between the ages of 20 and 75. However, deaths and ICU admissions tend to increase with age. (Graph 1).

**Graph 1.** Absolute number of hospitalizations, ICU admissions, and deaths in the United States as of March 16, 2020, CDC MMWR

Cases and hospitalizations were on the decline at the end of summer 2020. However, the overall weekly hospitalization rates in the United States have increased since the end of September (MMWR week 39, see Graph 2), driven mostly by adults over 18 years of age.

**Graph 2.** Weekly COVID-19-associated hospitalization rates by age group – COVID-NET, March 1 – October 24, 2020

#### *Time from symptom onset to death*

Data assessing the time course from onset of symptoms to death or time to recovery remain limited and generally do not include vital sign measures in the community. After onset of symptoms, the highest probability of death occurs just under 12 days, so there may be time after symptom onset to predict the likelihood of clinical decline and guide clinical intervention in many patients.

Currently, predictors of hospitalization across the lifespan remain general, demographic and largely intuitive. For example, individuals with advanced disease or multi-morbidity are at increased risk for poor outcomes when infected with COVID-19. A major goal of this work is to identify novel digital biomarkers that will enable early identification of patients who are likely to have severe disease while still in the community. This early identification could allow for more timely and aggressive supportive care, potentially reducing more severe disease and poor outcomes.

#### *Digital biomarkers and algorithm development using large databases*

There is a body of research utilizing commercially available wearable devices (e.g., Fitbit) that seeks to identify biomarkers that could predict infection ahead of noticeable symptoms. There is another avenue of research utilizing large, extensive preexisting databases to find and validate risk prediction algorithms that can estimate hospital admissions and death in COVID-19 infected adults. We plan to utilize already existing population-based algorithms and combine these with continuously collected vital signs from our medical-grade, remote monitoring wearable device. Unlike Fitbit or other commercially available wearables, the quality of observations from Current Health's remote monitoring device is much higher than so it can be used like a hospital monitor in the community. The Current Health device also stores the raw waveforms, allowing for retrospective audit of observation quality.

To our knowledge, this will be the first effort to apply these advanced models utilizing continuously collected, high-quality vital signs in the community, for the prediction of COVID19 disease progression.

## Research Objective and Outcomes

The overall objective of this contract is to train, develop, validate and release a digital biomarker-based algorithm that, in COVID-19 PCR or antigen positive patients, within 30 days of a positive test:

1. **Primary Outcome:** predicts likelihood of requiring a stay in hospital of 24 hours or longer
2. **Secondary Outcomes:**
  - a. Predicts likelihood of being admitted to ICU for either non-invasive (CPAP, BiPAP, high flow nasal oxygen), invasive ventilation or vasopressor support.
  - b. Predicts likelihood of death.
3. **Tertiary Outcomes:** Provides successful delivery, setup, daily interface engagement, and compliance with wearing of the device

## Methods

### Study Design

This study will be broken down into a pilot phase, followed by two stages of data collection. We will recruit, consent, and enroll approximately 2050 participants with a COVID-19 positive test over the course of the study. In the pilot phase and stages one and two, the following methods will apply.

Participants will be asked to wear the Current Health remote patient monitoring device for up to 30 days. Participants will also be provided with a Current Health tablet with an application installed. The tablet is not password protected, but no responses are stored locally, and they are associated with vital signs via the Current Health dashboard. The participant will be asked to complete a welcome survey on the first day of participation. The tablet will remind the participant each day to answer a brief series of questions about their symptoms and decisions on the tablet. The welcome and daily surveys include the content below:

Welcome Survey: Welcome! Today is your first day in Community by Current Health's COVID-19 Study. We need to collect some information about you. We will only ask these questions **one time**. This survey should take **less than 5 minutes to complete**.

Thank you again for taking part in this study. With your help our researchers will gain a better understanding of COVID-19 and be able to predict recovery and progression.

- 1) What is your date of birth?
- 2) What is your sex? Male/Female/other or prefer not to specify

If Female

- 1) To your own knowledge are you currently pregnant?
- 2) Do you have menstrual periods?
- 3) Are you:
  - Pregnant or breastfeeding
  - Taking hormonal birth control
  - Undergoing menopause or post-menopausal - Highly active (working out, training, fitness, etc.)
- 4) When was your last period?
- 3) What is your occupational category? Healthcare (doctor, nurse, dentist, etc.)  
Service industry (food service, grocery, mechanic, plumber, etc.)  
Retail  
Office – able to work from home  
Office – unable to work from home  
Currently unemployed  
Student – remote  
Student – attending class in person
- 4) What is your household make-up?  
Living alone  
Living with people
- 5) Do other members of your household currently have COVID-19? Y/N
- 6) Are any other members of your household enrolled in Community by Current Health's COVID-10 Study? Y/N
- 7) What is your self-identified race/ethnicity?  
White Hispanic

White Non-Hispanic  
 Black or African American  
 Asian  
 American Indian or Alaska Native  
 Native Hawaiian and Pacific Islander 8)

What is your height?

9) What is your weight (in pounds)?

10) Do you have **asthma**? Y/N

11) Do you have **cancer**? Y/N

12) Do you have **chronic obstructive pulmonary disease (COPD)**? Y/N

13) Do you have **diabetes**? Y/N

14) Do you have a **heart condition**? Y/N

15) Do you have **high blood pressure**? Y/N

16) Do you have **kidney disease** or **reduced kidney function**? Y/N

17) Have you ever had an **organ transplant**? Y/N

18) Do you have **sickle cell disease**? Y/N

19) Are you a **smoker**? Y/N

20) Do you take **beta blockers**? Beta blockers are medicines designed to reduce heart rate, which can affect vital sign readings. For example: Tenormin, Cardiacor, Emcor, Betaloc, Inderal, or Angilol.  
 Y/N

21) Please enter any feedback about this survey:

Thank you for filling out your welcome survey! Your responses have been recorded.

Daily Survey:

Each day Current Health will ask you a **brief series of questions** about symptoms and decisions that may be related to COVID-19. Your daily response and information collected from the wearable device will create the most accurate picture of your health. This survey should take **less than 5 minutes** to complete.

1) In the **past 24 hours**, did you have (or continue to have) any of the following symptoms:

- ✦ loss of smell or taste
- ✦ dry cough
- ✦ sore throat
- ✦ fever or feeling feverish
- ✦ chills
- ✦ muscle aches
- ✦ diarrhea
- ✦ nausea
- ✦ other, please specify (free text)

[FOR EACH YES] Is your <symptom> better or worse than yesterday?

- ✦ Categorical scale: Much worse, Worse, The same, Better, Much better

- 2) Due to how you are feeling **today**, do you plan to speak to a health care provider?
- 3) Due to how you are feeling **today**, do you plan to go to the hospital?
- 4) Do you feel as though you have completely recovered from COVID-19 as of today?

Thank you for completing your daily survey! Your responses have been recorded.

For our study participants, data will be collected “blind”. The participant will not be able to see their data in real time, and no data will be reviewed or acted upon by the study team unless there is a clinically indicated trigger elicited by the system. These triggers exist to prompt the capture of study-specific information, not to direct patient care.

1. Reduction in SpO2 below 88% for 60 minutes
2. Increase in pulse rate to more than 90 beats per minute for 60 minutes with minimal body movement (Current Health motion score < 2)
3. Increase in respiratory rate to more than 25 breaths per minute with minimal body movement (Current Health motion score < 2)

In these instances, participants will be contacted and asked the following two to three questions:

We cannot provide you with any medical advice but would like to ask you a few questions. First, have you experienced any new signs or symptoms including:

Shortness of breath  
Chest pain or pressure  
New or worsening cough  
Fever or feeling feverish  
Chills  
Headache  
Sore throat  
Muscle aches or joint pain  
Abdominal pain  
Diarrhea  
Nausea  
Other, please specify

If yes, to any symptom:

- Do you consider the symptom to be mild, moderate, or severe (worst ever)?

- Do you intend to seek medical care at an emergency room, urgent care, or hospital in the near future?
- If no:
- Has your device been working properly, or has it been damaged in any way?

Throughout the study, if a participant believes they have recovered from COVID-19 for any of the reasons listed below and tells the study team they will be resuming normal life and would like to exit the study, we will consider these participants fully compliant. COVID-19 recovery would be considered in any of the following situations:

1. Participant receives a follow-up COVID-19 PCR test that is negative
2. Participant was asymptomatic and isolated for 14 days without symptoms
3. Participant was symptomatic and onset of symptoms was at least 14 days prior with the last three days symptom free

Conversely, if a participant feels that they are experiencing severe symptoms related to SARS-CoV-2/COVID-19 that warrant a visit to the hospital or urgent care facility (which will be also evident by our questionnaire), the participant will be instructed to contact their healthcare provider, contact a nearby hospital to arrange for appropriate assessment, or call 911 if an emergency. We will not provide medical advice, or a real-time monitoring service, as this will likely bias the outcomes of the trial. This will be made explicitly clear to participants in the Informed Consent Form and process of consent. The outcome of that visit will be captured by a study team member.

A study participant will be considered fully adherent to study protocol if they:

- Wear the device for at least 20 hours a day, at least 6 days a week up to 30 days
- Answer the questions on the tablet at least 6 days a week up to 30 days
- Return the wearable device kit and tablet

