# 5. Study Objectives and Endpoints and Hypotheses

## 5.1. Study Objectives, Endpoints, and Outcomes

The overall objective of this study is to train, develop, validate and release a digital biomarker-based algorithm that, in COVID-19 PCR or antigen positive participants, within 30 days of a positive test:

1. Primary Outcomes:
  - a. Predicts likelihood of requiring a stay in hospital of at least 24 hours
  - b. Predicts likelihood of recovery from COVID-19 defined as:
    - i. For asymptomatic participants: 14 days without symptoms following positive test
    - ii. For symptomatic: at least 14 days since onset of symptoms, with the last three days symptom free
2. Secondary Outcomes:
  - a. Predicts likelihood of being admitted to ICU for either non-invasive (CPAP, BiPAP, high flow nasal oxygen), invasive ventilation or vasopressor support.
  - b. Predicts likelihood of death.
3. Tertiary Outcomes: Successful delivery, setup, daily interface engagement, and compliance with wearing of the device

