Smoker	smoker	Binary: Yes, No
Intake survey feedback	intake_survey_feedbackk	Long free text
†Daily Survey		
Loss of smell or taste	loss_smell_taste	Binary: Yes, No
Is your loss of smell or taste better or worse than yesterday?	loss_smell_taste_likert	Categorical: Much worse, Worse, The same, Better, Much better
Dry cough	dry_cough	Binary: Yes, No
Is your dry cough better or worse than yesterday?	dry_cough_likert	Categorical: Much worse, Worse, The same, Better, Much better
Sore throat	sore_throat	Binary: Yes, No
Is your sore throat better or worse than yesterday?	sore_throat_likert	Categorical: Much worse, Worse, The same, Better, Much better
Fever or feeling feverish	fever	Binary: Yes, No
Is your fever better or worse than yesterday?	fever_likert	Categorical: Much worse, Worse, The same, Better, Much better
Chills	chills	Binary: Yes, No

Are your chills better or worse than yesterday?	chills_likert	Categorical: Much worse, Worse, The same, Better, Much better
Muscle aches	muscle_aches	Binary: Yes, No
Are your muscle aches better or worse than yesterday?	muscle_aches_likert	Categorical: Much worse, Worse, The same, Better, Much better
Diarrhea	diarrhea	Binary: Yes, No
Is your diarrhea better or worse than yesterday?	diarrhea_likert	Categorical: Much worse, Worse, The same, Better, Much better
Nausea	nausea	Binary: Yes, No
Is your nausea better or worse than yesterday?	nausea_likert	Categorical: Much worse, Worse, The same, Better, Much better
Are there any other symptoms or differences in health you would like to report?	daily_survey_feedback	Long free text
Will you speak to a healthcare provider due to worsening symptoms today?	self_reported_provider_care	Categorical: Yes, No, Maybe
Will you go to the hospital due to worsening symptoms today?	self_reported_hospital	Categorical: Yes, No, Maybe
Do you feel as though you have completely recovered from COVID-19 as of today?	self_reported_recovery	Categorical: Yes, No, Maybe

\*Participant Intake Survey questions are to be completed by participant one time.

†Daily Survey questions are asked once a day at the same time each day.

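### The daily survey has no pre-COVID symptom baseline, yet SAP recovery requires absence of symptoms, so background symptoms can be miscoded as late or no recovery

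*Combined protocol and SAP*

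**What the plan says.** **How symptoms are recorded.** In the protocol (Methods, Study Design), Daily Survey item 1 asks "did you have (or continue to have) any of the following symptoms" in the past 24 hours. The list includes dry cough, muscle aches, diarrhea and nausea. The introduction to the survey speaks of "symptoms and decisions that may be related to COVID-19". Each Yes leads to one follow-up, which compares with the day before; SAP 8.5 gives the example "Is your dry cough better or worse than yesterday". SAP 8.5 stores each symptom as Yes/No. The welcome survey records diagnoses such as asthma and COPD, plus smoking and pregnancy, but not usual symptoms.

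**How recovery is defined.** SAP 5.1 lists a second primary outcome: "Predicts likelihood of recovery from COVID-19 defined as" either 14 days without symptoms after the positive test (asymptomatic participants) or "at least 14 days since onset of symptoms, with the last three days symptom free" (symptomatic participants).

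**Who codes it.** Under SAP 9.1 the CRA ascertains outcomes, and recovery is entered directly as Yes/No with no derivation. No data source is named. In the SAP 6.6 schedule, the daily survey is the only listed task that is described as recording symptoms.

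**Contrast in the same protocol section.** The call made after a vital-sign trigger asks "have you experienced any new signs or symptoms including" a list that contains "New or worsening cough".

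**The concern.** A person with a usual dry cough or pregnancy nausea can truthfully answer Yes to item 1 after COVID-19 has resolved. The introduction does not tell that person to answer No. The follow-up does not help, because a stable chronic cough and a persisting COVID-19 cough can both be reported as unchanged since yesterday. With no recorded baseline, neither the CRA nor an analyst can separate the two later from the survey data.

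The error would not be random. Background symptoms go with conditions such as asthma, COPD, smoking and pregnancy, which the welcome survey collects, and SAP 9.2 runs medical history through the algorithm together with symptoms. Miscoded recovery would therefore be differential by predictors: the model would find an association between a condition and non-recovery that the outcome coding had created, and its apparent discrimination for recovery would rise. The split between symptomatic and asymptomatic participants in SAP 5.1 is open to the same error.

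**Working it through.** The plan gives no figure for recovery or for chronic symptoms, so there is nothing to reproduce. Its 10% event rate (SAP 6.3) concerns hospitalization or intensive care. Every rate below is an assumption, used only to show the possible size.

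**1. Does a background symptom block recovery?**

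Suppose COVID-19 symptoms are over and a background symptom is reported each day with probability q, independently between days. Recovery needs three symptom-free days in a row, ending on day 14 or later, so days 12 to 30 (19 days) count. Let a0, a1 and a2 be the probabilities that the current symptom-free run has length 0, 1 or 2 with no success so far. Each day:

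- a0 becomes q(a0 + a1 + a2)
- a1 becomes (1 − q) × the previous a0
- a2 becomes (1 − q) × the previous a1
- the success probability grows by (1 − q) × the previous a2

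If only the last three days of the 30 count, the probability is (1 − q)³.

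| q | Any three-day run ending on days 14–30 | Final three days only |
|---|---|---|
| 0.25 | 0.99 | 0.42 |
| 0.50 | 0.77 | 0.13 |
| 0.75 | 0.19 | 0.016 |
| 0.90 | 0.015 | 0.001 |
| 1 | 0 | 0 |

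An occasional symptom mostly delays recovery, if the rule accepts any qualifying run. A near-daily one mostly prevents it.

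**2. What association would this create?**

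Assumptions: true non-recovery is 10% in everyone; 20% have a recorded condition; a fraction f of these have a persistent background symptom and are all miscoded as not recovered; nobody else is miscoded.

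- Non-recovery with the condition: p1 = 0.10 + 0.90f. Without it: p0 = 0.10.
- Odds ratio = [p1/(1 − p1)] / [0.10/0.90].
- Coded non-recovery overall: N = 0.20p1 + 0.80 × 0.10.
- AUC of the condition alone = ½[0.20p1/N + 0.80 × 0.90/(1 − N)].

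| f | p1 | N | Odds ratio | AUC |
|---|---|---|---|---|
| 0.15 | 0.235 | 0.127 | 2.8 | ½(0.370 + 0.825) = 0.60 |
| 0.25 | 0.325 | 0.145 | 4.3 | ½(0.448 + 0.842) = 0.645 |
| 0.50 | 0.550 | 0.190 | 11.0 | ½(0.579 + 0.889) = 0.734 |

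The range of f means that 3% to 10% of all participants have such a symptom (0.20 × 0.15 and 0.20 × 0.50). The false share of coded non-recoveries is then 0.027/0.127 = 21% to 0.090/0.190 = 47%.

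**3. If the CRA corrects half of these cases**

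Halving f to 0.075, 0.125 and 0.25 gives p1 = 0.1675, 0.2125 and 0.325. The odds ratios are about 1.8, 2.4 and 4.3, and the AUCs about 0.55, 0.58 and 0.645.

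On the SAP 5.2 benchmarks (0.55 to 0.65 moderate, 0.65 to 0.75 acceptable), a condition with no true effect on recovery could score as moderate or, at the upper end, acceptable.

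**The case against.** The strongest objection is that no text derives recovery from item 1. The CRA enters it directly (SAP 9.1) and could discount a long-standing cough. The survey also asks daily whether the participant feels fully recovered from COVID-19, and the protocol accepts a negative follow-up PCR as recovery. A reader might infer that people with a chronic symptom can never be counted as recovered, or that they will certainly be miscoded. The documents do not support that: the link to the survey is unstated, and under the three-day rule a zero chance requires a listed symptom every day. The listed cough is also a dry one; any other kind enters only as free text. This part of the objection stands.

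It does not close the gap. The self-reported recovery item is a separate variable outside the SAP 5.1 definition. The PCR route is absent from SAP 5.1, and no follow-up test is in the SAP 6.6 schedule. If the CRA asks by telephone instead, SAP 5.1 still gives no rule for pre-existing symptoms.

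The assumptions behind the odds ratios are also unfavorable to the plan: all affected people fall in the condition group, all are miscoded, and conditions that the survey records separately are pooled. This is why the result is a range and an illustration.

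The consequences are limited too. Recovery is a primary outcome only in the SAP, Stage 1 does not name it among the network's targets, and the 75% hypothesis in SAP 5.2 concerns hospitalization. Nor would the network necessarily treat a condition as a cause of non-recovery, since the protocol fixes arc direction from literature and clinical knowledge. The supportable word is association.

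Finally, the trigger call serves another purpose, acute change after an alarm, so the difference in wording is not itself a contradiction. It shows only that suitable wording is already in use.

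**Conclusion.** The point holds as a gap in measurement and definition. The daily item has no baseline reference, no survey supplies one, and a primary outcome of the SAP rests on absence of symptoms without saying which symptoms count or where the CRA finds them. If the rule is applied literally to the survey, frequent background symptoms can delay or prevent a recovery code, differentially by predictors.

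The size cannot be known from the documents. With the assumptions stated above, the spurious odds ratio is about 2.8 to 11 and the AUC about 0.60 to 0.73, and less if the CRA corrects some cases. The hospitalization outcome and its hypothesis stand, apart from some noise in the symptom inputs. This is a cheap improvement that should be made, because an unrecorded baseline cannot be reliably reconstructed afterwards.

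**What to change.** 1. Reword Daily Survey item 1 to ask about listed symptoms that are new, or worse than was usual for the participant before COVID-19, in line with the trigger call. Alternatively, keep the item and add one question to the welcome survey on which listed symptoms the participant usually had before COVID-19.
2. In SAP 5.1 and 9.1, define 'symptom free' and 'asymptomatic' by that item (or by item 1 read against the recorded baseline), and name it as the CRA's source for recovery.
3. Reconcile the recovery definitions in the protocol's Study Design section and SAP 5.1, which differ on the negative PCR route.

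The cost is a phrase or one question on the tablet and a few sentences in the SAP. Participants must judge what is usual for them, which adds a little recall error. The pilot is meant to bring out user issues that affect the data, so the change fits there. Symptom data already collected under the present wording should be flagged as not equivalent.

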## 6.6. Timing of Outcome Assessments

The frequency and timing of all the relevant study assessments is considered from the time the participant CH kit arrives to 30 days of observation or a met outcome.

Study Task	Timeline
Kit Setup	Day 1
Participant Intake Survey	Day 1 to Day 3
*Daily Survey	Daily
CRA Adherence Checks	Day 1 to Day 30 ongoing
Vital signs captured by CH wearable	Day 1 to Day 30 ongoing
Outcome Verification	Day 1 to Day 30 ongoing and 30 days after observation period ends

\*Daily symptom questionnaire will close if not completed within a given number of hours. Participant will still be able to fill out the following day's daily symptom questionnaire.

Variables collected from study assessments will be generally as follows:

- Demographic – Categorical
- Medical history and medication – Boolean
- Symptom presence – Boolean (“Much better” to “Much worse”)
- Symptom severity – Ordinal categorical

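### The daily survey has no structured item for shortness of breath or chest pain; the plan asks about them systematically only after a vital-sign trigger

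*Combined protocol and SAP*

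**What the plan says.** **Daily survey (protocol, Study Design).** Eight symptoms are named: loss of smell or taste, dry cough, sore throat, fever, chills, muscle aches, diarrhea and nausea. A free-text entry covers anything else. Each symptom reported is rated only as "better or worse than yesterday". Items 2 and 3 ask whether the participant plans to speak to a provider or go to the hospital.

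**Trigger call (same section).** Three vital-sign conditions prompt a call: low SpO2, high pulse rate or high respiratory rate. The protocol says: "In these instances, participants will be contacted and asked the following two to three questions". The symptom list read out begins with "Shortness of breath" and "Chest pain or pressure". A participant who reports any symptom is then asked: "Do you consider the symptom to be mild, moderate, or severe (worst ever".

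**Statement about the questionnaire (same section).** For a participant who feels severe symptoms, the protocol speaks of symptoms "that warrant a visit to the hospital or urgent care facility (which will be also evident by our questionnaire".

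**SAP 8.5.** Each of the eight daily symptoms has a yes/no variable and a change variable coded "Categorical: Much worse, Worse, The same, Better, Much better". There is one free-text field, and there are three-level variables for planned provider contact, planned hospital visit and self-reported recovery. No variable is listed for the trigger-call answers.

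**Use of the data.** SAP 9.2 (Stage 2) lists symptom data among the inputs run through the algorithm. SAP 5.1 makes recovery a primary outcome. For symptomatic participants it requires three symptom-free days; for asymptomatic ones, 14 days without symptoms.

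**The concern.** The sponsor's call script shows that the study team regards shortness of breath and chest pain as worth asking about when a participant may be deteriorating. The instrument that every participant completes every day does not ask about them. As written, the structured record of these symptoms exists only for participants whose vital signs have already crossed a threshold.

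Two things are at stake. First, the network has no dedicated daily variable for two symptoms that could plausibly help predict hospital stay and ICU support. If the trigger-call answers were used instead, whether they are missing would depend on SpO2, pulse and respiratory rate, which are themselves predictors. Second, SAP 5.1 ties symptom freedom to no list. If it were judged from the eight named items, a participant whose only remaining symptom was breathlessness could be counted as symptom free. Symptoms that were not asked about cannot be recovered reliably afterwards.

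**Working it through.** **Step 1. Compare the two symptom lists.** Dry cough (daily) is matched with new or worsening cough (call).

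| | Daily survey and SAP 8.5 | Trigger call |
|---|---|---|
| Named symptoms | 8 | 11 |
| Shared | 7 | 7 |
| In this list only | loss of smell or taste | shortness of breath, chest pain or pressure, headache, abdominal pain |
| Symptoms graded mild, moderate or severe | 0 of 8 | any reported |
| Who is asked | everyone, daily | only after a vital-sign trigger |
| Listed SAP 8.5 variable | presence and change | none |

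Four symptoms are therefore in the call only, and they include the first two that the call asks about.

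**Step 2. Ask whether another route captures them.** The daily free-text entry does, if the participant thinks to type them. The available text gives no rule for coding it. Daily items 2 and 3 record intent to seek care, not which symptom is present.

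**Step 3. Illustrate what a structured item might add.** The documents give no inputs for this, so all of them are assumed. The other predictors are given a binormal score with AUC 0.72. Shortness of breath is a binary marker, present in a proportion s of hospitalized participants and f of the others, and is combined with the score by likelihood ratio.

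- With d = √2 × Φ⁻¹(0.72), the combined AUC is the sum, over the four marker combinations, of p₁ × p₀ × Φ((d² + m₁ − m₀)/(d√2)). Here m is the marker's log likelihood ratio and p its probability, for a hospitalized (1) and another (0) participant.
- Marker independent of the score given outcome (best case): s = 0.50, f = 0.15 gives 0.791 (gain 0.071); 0.30 vs 0.10 gives 0.754 (gain 0.034); 0.60 vs 0.10 gives 0.843 (gain 0.123).
- Only 30% of cases typed as free text and coded, for 0.50 vs 0.15: s becomes 0.15 and f becomes 0.045, giving 0.738 (gain 0.018).
- Latent correlation of 0.5 with the score within each outcome group: the gain falls to about 0.035 for 0.50 vs 0.15 and about 0.01 for 0.30 vs 0.10.

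The correlated case is the more realistic one for breathlessness, because SpO2 and respiration rate are measured continuously. The gain tends to zero as those signals come to carry the same information.

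**Step 4. Check the burden on the sample size.** SAP 6.3, Calculation 2, uses φ = 0.1, P = 30 and MAPE = 0.05:

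n = exp[(−0.508 + 0.259 ln 0.1 + 0.504 ln 30 − ln 0.05)/0.544] = 755.9, which reproduces the stated 756.

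- Four presence items, P = 34: 849.
- Four presence items and four change scores, each counted as one parameter, P = 38: 941.
- The same with one overall daily severity grade, P = 39: 964.

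All three are below the 1,000 to be recruited for training. However, Appendix B states the formula for P of 30 or fewer, so they are extrapolations. SAP 7.3.2 also restricts training to adherent participants, who may number fewer than 1,000.

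**The case against.** Several stronger readings are tempting, and the documents do not support them.

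- **That the statement about the questionnaire is false.** It concerns a participant who feels that a visit is warranted. Daily items 2 and 3 ask about care-seeking plans every day without any trigger, and SAP 8.5 gives both answers a variable. The residue is minor: the daily survey does not name urgent care.
- **That the SAP promises a severity variable and then omits it.** SAP 6.6 does list "Symptom severity – Ordinal categorical". But the line above attaches the better-to-worse scale to a Boolean presence variable, which cannot be right. The scale plausibly belongs to the severity line, and SAP 8.5 then supplies it. This is a labelling query.
- **That recovery will be misclassified.** SAP 9.1 has the clinical research associate ascertain outcomes directly. Nothing derives recovery from the eight items, so the harm is conditional.
- **That hospital stays will be missed.** Outcome verification and the next-of-kin contact cover them.
- **That the model will fall short of its AUC bar of 0.75 without these items.** The base of 0.72 was chosen for illustration. From a base of 0.78 the bar is cleared without them.

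Three further objections have some force. SAP 8.5 is not exhaustive, since it also omits the beta-blocker question in the welcome survey; absence from it does not prove that call answers go unrecorded. The summary of SAP changes refers to a section 9.5, while the available section 9 ends at 9.2, so a coding rule for free text may exist in text not seen here. The protocol also allows variables to be transformed iteratively during training. None of this alters the content of the daily survey, which the protocol sets out in full and which does not ask about these symptoms by name.

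**Conclusion.** The point holds in a limited form, as a cheap improvement. Shortness of breath and chest pain or pressure have no structured daily item and no dedicated variable in SAP 8.5. They are asked systematically only after a trigger that depends on other predictors. This rests on comparing the two scripts with the variable table and needs no numerical assumption.

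The size of the consequence is not established. The illustrative AUC gains, about 0.01 to 0.12 with a structured item, rest wholly on assumed prevalences, an assumed base AUC and assumed dependence on the other predictors. The effect on recovery depends on how symptom freedom is judged in practice. The case for acting is that the remedy is small and the information cannot be reliably reconstructed later.

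**What to change.** Before Stage 1 begins:

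1. Add yes/no items for shortness of breath and for chest pain or pressure to the daily survey and the SAP 8.5 table, each with the existing change scale. Add headache and abdominal pain in the same way, so that the daily survey covers the whole call list.
2. State in SAP 5.1 that symptom freedom for the recovery outcome is judged on this extended list.
3. State in the SAP that trigger-call answers are not used as a substitute predictor, because they exist only after a vital-sign trigger.
4. Optionally, add one overall mild, moderate or severe grade per day, and correct the two symptom lines in SAP 6.6 to match.

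**Cost.** There are four extra answers a day when none of the new symptoms is present, and at most 4 + 4 = 8 when all are; the optional grade adds one. The survey is described as taking less than five minutes. The longer survey might slightly reduce adherence, which matters because only adherent participants enter training and testing. There are a few more candidate parameters, as costed above. The new items will be missing by design for pilot participants enrolled before the change. No contact or real-time review is added, so the decision not to offer monitoring is unaffected.
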